4 METHODOLOGY

- 4.3 Study Details and Procedures
- 683 **Study Design and Sampling**: This is a single arm, open-label Phase I, non-randomized study.
- Participants meeting the inclusion criteria will be sequentially enrolled.

685

681

- 686 **Study Population:** The study population will be up to 16 women 18 years or older living in
- Kisumu County in Kenya, in order to have 12 fully evaluable participants, our desired sample
- size. Fully evaluable participants are those who receive artesunate inserts for 5 consecutive days
- and undergo blood draws before and after receiving artesunate at all the timepoints per study
- 690 protocol. Enrollment will stop once data from 12 fully evaluable participants are obtained. No
- more than 16 participants will be enrolled.

692 693

694

695

696

697

698

699 700

Inclusion Criteria

- 1. Age 18 years or older
- 2. Negative pregnancy test at screening
- 3. Weight ≥50 Kg at study entry*
- 4. Willingness to use contraception (hormonal or barrier) during the 5-day study dosing phase if of childbearing age (less than 50 years of age)
- 5. Ability and willingness to provide informed consent
- 6. Plan to reside in the study location during the study period
- *Justification for weight criteria: A minimum body weight of 50Kg will meet the planned artesunate dosing of ≤ 4 mg/Kg for which excellent safety data is available.

702 703 704

705

706

707

708

709

710

711

712

713

701

Exclusion Criteria

- 1. Current pregnancy or breastfeeding status
- 2. History of total hysterectomy
- 3. Known allergy to Artesunate
- 4. Have a medical comorbidity that in the opinion of the investigator would interfere with study participation
- 5. Currently receiving artemisinin-based agents for malaria treatment or completed artemisinin-based treatment within the previous 3 days.*
- Male at birth
 - 7. Current use of efavirenz antiretroviral therapy
- 714 8. Positive malaria antigen test at screening
- *Based on dihydroartesunate (artesunate's active metabolite) half-life of between 0.5-1.5 hours²⁹
- 717 **Study Location:** The study will be carried out at the Lumumba Sub-County Hospital and at the Victoria Biomedical Research Institute in Kisumu, Kenya.
- Recruitment: Participants will be recruited from among women in the general population within the vicinity of the study location, including within health facilities in Kisumu County in Kenya.

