4.4 Specimen collection, processing, storage and analysis

For each participant, ~2.5 ml of blood will be collected at each timepoint at baseline (Day 1), and on day 5 prior to administration of intravaginal artesunate (time 0), and at 15, 30min, 1h, 3h, and 6h after administration. Blood will be collected in gold/yellow top tubes and centrifuged to plasma which will be stored at -80°C until analyzed. Samples will be stored at Kenya Medical Research Institute (KEMRI)-affiliated accredited laboratories in Kisumu, Kenya, with cold chain maintained from collection to storage until shipping for analysis. All study staff as well as laboratory staff will be trained on study SOPs.

DHA and artesunate plasma testing: Specimens will be tested at the Walter Reed Army Institute of Research, (WRAIR) Division of Experimental Therapeutics laboratory in Maryland, USA which has validated DHA and artesunate assays. Analysis will be led by [name], D.O Chief of Clinical at the Walter Reed Army Institute of Research and the Clinical Pharmacology Fellowship Program Director. Plasma samples will be shipped under cold chain and remain frozen at at -80°C in WRAIR laboratory facilities until ready for analysis. Analysis will be performed using a validated high-performance Liquid Chromatography Mass Spectrometry (LCMS) assay at WRAIR with limits of quantification of Artesunate and DHA of approximately 80nM and 70 nM, respectively. 31,71 Quality control (QC) samples will be included with each assay batch, with a requirement that the run is acceptable only if the QC is within +/-15% of the nominal value. 35 The WRAIR Division of Experimental Therapeutics, Drug Metabolism and Disposition has over 75 years' experience with drug and product development, having achieved U.S FDA approval of 9 malaria drugs and more than 65 investigational new drug applications. All appropriate material transfer agreements and shipping licenses will be obtained from all relevant regulatory bodies including the Amref ESRC before specimen shipping is done. All specimens will be destroyed following testing. Each sample will be assigned a unique code number, and no identifiable personal health information (PHI) will be on the specimen label.

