Pharmacokinetic analysis: Conventional pharmacokinetic parameters - AUC (0, infinity), half-life, apparent clearance, the volume of distribution, maximum plasma concentration (Cmax), time to Cmax will be determined from the plasma concentration-time data using noncompartmental analysis. Peak plasma concentration (Cmax) and time to reach peak concentration (tmax) for artesunate and DHA will be the observed values. The AUC of AS will be calculated by linear trapezoidal summation with extrapolation to infinity. With respect to

DHA, AUC will be calculated to the last drug measurable time point. The elimination rate constant (β), will be calculated from the slope of the terminal phase of the log concentration-time profile, and the elimination half-life (t1/2) calculated from the ratio of ln 2/ β . Other PK parameters will be calculated using standard model-independent formulae.³⁹ The estimates of PK parameters for DHA will assume complete conversion of AS to DHA as reported previously.³⁵ Data will be plotted graphically and analyzed using statistical software. Data will be presented as mean with standard deviation (SD).

Compliance Statement: Biospecimen collection for this study will be conducted in full accordance with all applicable University of North Carolina (UNC) Research Policies and Procedures including Good Clinical Practice (CGP) policies, and all applicable Federal and state laws and regulations including 45 CFR 46, and the Health Insurance Portability and Accountability Act Privacy Rule, as well as the in-country regulatory agencies including the Amref Ethics and Scientific Review Committee (ESRC), the Kenya Pharmacy and Poisons Board (PPB), the National Commission for Science, Technology & Innovation (NACOSTI) and any other regulatory bodies required in-country. Any episode of noncompliance will be documented. The investigators will perform the study in accordance with this protocol, will obtain consent, and will report unexpected problems in accordance with the UNC IRB Policies and Procedures and all federal requirements. Collection, recording, and reporting of data will be accurate and will ensure the privacy, health, and welfare of research participants during and after the study.

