Removal of Participants from the Study: Any participant who does not wish to participate in the study will be exited from the study at any time they prefer. Additionally, participants who fail to adhere to significant protocol requirements, including failure to meet inclusion/exclusion criteria, use of prohibited concomitant medications, incident pregnancy, or other reasons that in the opinion of the Principal Investigator may affect participant safety may be removed from the study. The Investigator will determine if a protocol violation results in withdrawal of a participant. All protocol violations will be reported to the relevant governing IRBs.

Participants who permanently discontinue study product and follow-up prior to study completion will be asked to complete an early withdrawal visit, if willing, during which any AEs will be assessed. If study removal occurs due to pregnancy, participants will be referred to the nearest preferred prenatal facility for pregnancy care.

Replacement of Participants: A sample size of N=12 participants are needed for the primary aims of PK analysis. To allow for potential drop offs or incomplete evaluation, up to N=16 participants will be consented and enrolled to have a sample size of N=12 fully evaluable participants, who will finish all study visits and have all specimens collected. Once the minimum sample size of N=12 of fully eligible participants is met, no additional participants will be enrolled or initiate study procedures.

 Participant Withdrawal: If a participant decides to withdraw from the study (and not just from protocol therapy) an effort should be made to complete and report study assessments as thoroughly as possible. At the time of withdrawal, the investigator should attempt to establish as completely as possible the reason for the study withdrawal.

- The participant should be asked if they are willing to allow for the abstraction of relevant information from their medical record in order to meet the objectives outlined in the protocol.
- A complete final evaluation at the time of the participant's study withdrawal should be obtained with an explanation of why the participant is withdrawing from the study.
- If the participant is noncompliant and does not return for an end of study follow up assessment, this should be documented in the eCRF.
- If the reason for removal of a participant from the study is an adverse event, the principal specific event will be recorded on the eCRF.

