4.5.2 Data Analysis Plans

- 1117 **Primary Outcome:** Plasma concentration versus time curve (AUC) of dihydroartemisinin
- 1118 (DHA) following five consecutive days of self-administration of 200mg Artesunate vaginal
- inserts (pessaries) among healthy women in Kenya.
- 1120 Primary Endpoint: Mean DHA AUC (ng*hr/ml) with standard deviation on Day 5
- 1121 Statistical analysis: Mean DHA AUC will be compared to historical studies after IV, oral and
- rectal administration among adults following similar dosing. Results will be analyzed using the
- student's t-test for one-sample observation and a p-value of 0.05 will be considered statistically
- 1124 significant.

1125 1126

Secondary Outcomes

- 1127 1.Plasma AUC of Artesunate following 5-day self-administration of 200mg Artesunate vaginal
- inserts (pessaries)
- 1129 Endpoint: Mean artesunate AUC (ng*hr/ml) with standard deviation on Day 5
- 1130 Statistical analysis: Mean artesunate AUC (ng*hr/ml) will be compared to historical studies after
- 1131 IV, oral and rectal administration among adults following similar dosing. Results will be
- analyzed using the student's t-test for one-sample observation and a p-value of 0.05 considered
- statistically significant.

1134

- 2. Maximum concentration of Artesunate (Cmax) following 5-day self-administration of 200mg
- 1136 Artesunate vaginal inserts (pessaries)
- 1137 Endpoint: Mean artesunate Cmax (ng/ml) with standard deviation on Day 5
- 1138 Statistical analysis: Mean artesunate Cmax (ng/ml) will be compared to historical studies after
- 1139 IV, oral, and rectal administration among adults following similar dosing. Results will be
- analyzed using the student's t-test for one-sample observation, and a p-value of 0.05 considered
- statistically significant.

- 3. Maximum concentration of DHA (Cmax) following 5-day self-administration of 200mg
- 1144 Artesunate vaginal inserts (pessaries)
- 1145 Endpoint: Mean DHA Cmax (ng/ml) with standard deviation on Day 5
- 1146 Statistical analysis: Mean DHA Cmax (ng/ml) will be compared to historical studies after IV,
- oral and rectal administration among adults following similar dosing. Results will be analyzed

PI: [name] UNIVERSITY OF NORTH CAROLINA Version 1.0 April 25, 2023

- 1148 using the student's t-test for one-sample observation and a p-value of 0.05 considered statistically 1149 significant.

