- 1219 (CTCAE 5.0) and the Division of AIDS Female Genital Adverse Events Grading Table
- 1220 Statistical Analysis: The counts of adverse events for each participant will be tabulated by
- severity (grades 1-5). The proportion of participants with a severe AE (grade 3 or higher) will
- be reported along the exact (Clopper-Pearson) one-sided upper 95% confidence bounds. The
- proportion of participants who report a severe AE (if any) will also be reported, along with an exact one-sided upper 95% confidence bound.

1225 1226 1227 - The at-risk period for safety will begin at study visit 1 (first artesunate use) and will continue through study visit 6 (4-10 days after last artesunate use). Safety data will be reported for all participants who start artesunate use.

- Pharmacokinetic analysis: Conventional pharmacokinetic parameters AUC (0, infinity), halflife, apparent clearance, volume of distribution, maximum plasma concentration (Cmax), time to
- 1232 Cmax will be determined from the plasma concentration-time data using noncompartmental
- analysis. 35,76 Peak plasma concentration (Cmax) and time to reach peak concentration (Tmax) for
- artesunate and DHA will be the observed values. The AUC of AS will be calculated by linear
- trapezoidal summation with extrapolation to infinity, and AUC time curve will start from drug
- administration to the last quantifiable observation. All parameters will be calculated using time
- in hours after the first drug administration. With respect to DHA, AUC will be calculated to the
- last drug measurable time point. The elimination rate constant (beta) will be calculated from the
- slope of the terminal phase of the log concentration-time profile, and the elimination half-life

- 1240 (t1/2) calculated from the ratio of ln 2/beta. Other PK parameters will be calculated using
- standard model-independent formulae.³⁹ The estimates of PK parameters for DHA will assume
- 1242 complete conversion of AS to DHA as reported previously.³⁵ Data will be plotted graphically
- and analyzed using statistical software. Data will be presented as mean with standard deviation
- 1244 (SD).
- 1245 **4.6 Community Engagement Plan**
- 1246 The target population will be sensitized about the study through talks in public forums including
- health facilities within Kisumu County where the study will be done.
- 1248 4.7 Study Limitations, Risks and Mitigation of Risks

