Risk of developing artemisinin resistance for malaria treatment: As discussed in section 3.1, the dosing used for intravaginal use is much lower than that used for the rectal artesunate formulation for malaria treatment. Compared to the rectum, vascularity at the vaginal and cervix is significantly less hence likelihood of systemic exposure is exceedingly low. As such, minimal to no appreciable levels of the active substance are expected following intravaginal use of artesunate at the planned dosing and frequency. The objective of this study is to confirm this.

1343 1344 1345

1346

1347

1348

1349

1350

1351

1352

1353

Risk of breach of confidentiality: Other small risks associated with study participation include a risk of breach of confidentiality during the study. This will be minimized through using only a unique participant identification number, and not participant names or other identifiers. Study participation will include data collection regarding basic medical history. The risk of this is minimal as questions asked will be routine medical questions. However, all efforts will be made to reduce the risk of distress to participants including using experienced interviewers, offering interviews in privacy for all participants, and reviewing the confidentiality of all answers at the beginning of data collection. Study staff will monitor participants for any signs of psychological distress and refer participants for additional counselling, as needed.

1354 1355

1358

1359

1360

1361

1362

1363

1364

1365

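### The primary DHA AUC stops at each woman's last measurable sample, with no rule for results below about 20 ng/mL; separately, the Day 5 sampling times conflict

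*Combined protocol and SAP*

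**What the plan says.** The endpoint line in Section 4.5.2 reads "Primary Endpoint: Mean DHA AUC (ng*hr/ml) with standard deviation on Day 5". It names no interval.

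The interval comes from the pharmacokinetic analysis paragraph in Section 4.4 (specimen collection and analysis). That paragraph opens with a general list that includes AUC from 0 to infinity. For the parent drug it says "The AUC of AS will be calculated by linear trapezoidal summation with extrapolation to infinity". For the metabolite it says "DHA, AUC will be calculated to the last drug measurable time point". Section 4.5.2 repeats the rule and counts time "in hours after the first drug administration. With respect to DHA, AUC will be calculated to the" last measurable point, although the serial profile follows the Day 5 dose.

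Section 4.4 gives "limits of quantification of Artesunate and DHA of approximately 80nM and 70 nM, respectively". Section 5.4 says that "minimal to no appreciable levels of the active substance are expected following intravaginal use of artesunate".

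Fully evaluable women are those who take five daily inserts "and undergo blood draws before and after receiving artesunate at all the timepoints per study" protocol (Section 4.3, Study Population), or those "who will finish all study visits and have all specimens collected" (Replacement of Participants). Both definitions turn on draws done, not on results obtained.

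The Day 5 sampling times appear in two versions:
- The synopsis, Protocol Summary, Section 1.7, Study Schema (2.4) and Visit 5 activities (4.2) give a pre-dose sample plus seven: 15 and 30 min, 1, 2, 4, 6 and 8 h.
- Section 4.4 gives a pre-dose sample plus five: 15 and 30 min, 1, 3 and 6 h. The Lay Summary counts six Day 5 draws, which fits 1 + 5 and not 1 + 7.

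**The concern.** An AUC that ends at the last measurable sample covers a different stretch of time in each woman, and the assay limit sets where it ends. When concentrations are high, little is lost. When they are near the limit, most of the curve can fall outside the integral, and a woman with no measurable sample has no end point and no AUC.

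That is the situation the protocol predicts. Such a woman still counts among the 12 and would not be replaced. Someone must then decide, with data in hand, whether she enters the mean as 0 or is left out. The mean is the figure the study carries into the malaria-resistance question, so neither the interval nor this choice should be left open.

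The sampling conflict is a separate defect. It decides which samples exist for the primary endpoint.

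**Working it through.** The plan gives no figure of its own for this point, so there is none to reproduce.

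**Inputs from the documents.** DHA limit 70 nM (4.4). Rectal 200 mg DHA means in healthy adults (1.3): Cmax 385.6 ng/mL, Tmax 1.80 h, half-life 1.21 h, AUC 965 ng·h/mL. The two sampling grids above.

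**Assumptions, not in the documents.** DHA molecular weight 284.35 g/mol. One-compartment curve with first-order input and a lag. Log-normal spread with CV 50% for AUC, 25% for half-life and 30% for ka; lag uniform on 0.5-1.6 h. Exposure set at fractions of rectal. Below-limit samples before the last measurable one set to 0. 20,000 simulated women per level.

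**Step 1, the limit.** 70 × 284.35 / 1000 = 19.9 ng/mL, about 5% of the rectal Cmax (19.9 / 385.6).

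**Step 2, the curve.** ke = ln 2 / 1.21 = 0.573 per h. For this model Cmax/AUC = ke·exp(−ke·tm), with tm = ln(ka/ke)/(ka − ke). Setting this to 385.6/965 = 0.400 gives ka = 3.41 per h and tm = 0.63 h. The lag is 1.80 − 0.63 = 1.17 h.

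**Step 3, the stated rule and a fixed interval on the 8 h grid** (AUC in ng·h/mL).

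| Exposure, % of rectal | Mean AUC to last as share of AUC(0, infinity) | Shortfall | Women of 12 with no quantifiable sample | Fixed 0-8 h: below limit = 0 / = limit | True mean AUC(0-8) |
|---|---|---|---|---|---|
| 100 | 93% | 65 | 0.0 | 928 / 977 | 933 |
| 50 | 86% | 69 | 0.0 | 450 / 519 | 466 |
| 25 | 71% | 70 | 0.04 | 207 / 300 | 233 |
| 10 | 35-42% | 63 | 2.1 | 61 / 188 | 93 |
| 5 | 13-39% | 42 | 8 | 15 / 164 | 47 |

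Where a range is shown, the lower figure counts women with no quantifiable sample as 0 and the upper leaves them out. At 10% exposure 17.8% of women have none: 12 × 0.178 = 2.1, and the chance of at least one is 1 − 0.822^12 = 0.90. At 5% the 0-or-omit choice alone changes the reported mean threefold (13% against 39%).

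**Step 4, dependence on shape.** Single curve shapes on the 8 h grid recover anywhere from 10% to 69% at 10% exposure. With a 4 h half-life the shares are about 68%, 63%, 43-53% and 8-43% at 100%, 50%, 25% and 10%. The shortfall at full exposure is then about 0.32 × 965 = 309, so the ceiling of 70 in the table belongs to the rectal half-life.

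**Step 5, the Section 4.4 times.** At full rectal exposure the total loss is about 262-265 ng·h/mL. In the same model AUC(0, infinity) is about 963, AUC(0-6) about 888, and the trapezoid on that grid with no assay limit about 749.
- Exposure after 6 h: 963 − 888 = 75.
- Trapezoid error from missing the peak: 888 − 749 = 139.
- Assay limit plus stopping rule: the remaining 49 or so.
- Sum: 75 + 139 + 49 = 263.

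**Step 6, the historical comparison.** The lowest historical DHA AUC quoted in Section 1.3 for IV, oral or rectal dosing is 965. At 25% exposure the true mean is 0.25 × 965 = 241 and the reported mean 0.71 × 241 = 171. At 10% they are 96.5 and 34-41. Both lie far below 965 whichever rule is used.

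**The case against.** The strongest reply is that the plan does define the AUC. A reader of the endpoint line alone might infer that no interval is named anywhere. The documents do not support that: Sections 4.4 and 4.5.2 both say where DHA AUC ends. What stands is that this end point is set by the data and the assay, and sits beside a listed AUC to infinity.

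A reader might also blame the stopping rule for the whole loss of about 262 ng·h/mL on the Section 4.4 times. Step 5 shows that only about 49 belongs to the limit and the stopping rule. The rest comes from the sparse grid and exposure after 6 h, so the sampling conflict is kept as a separate point.

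A third tempting reading is that the truncated AUC biases the test against historical values or would overturn it. The documents do not say whether the historical AUCs were truncated or extrapolated, so no like-for-like bias can be claimed. In the low range the protocol expects, the comparison would not reverse (step 6).

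It is also fair to say that the percentages rest on an assumed curve and exposure, that a large share of a small AUC is still a small amount, and that the time-origin wording is minor because every endpoint line says Day 5. All of this stands. None of it supplies the missing rule for below-limit results.

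**Conclusion.** The point holds and should be settled before analysis. The primary DHA AUC has an interval that varies by woman with the assay limit, and there is no rule for below-limit samples or for an evaluable woman with none above the limit. On the 8 h schedule with a rectal-shaped curve, the stated rule recovers about 93% of AUC to infinity at full rectal exposure and 35-42% at one tenth of it, where about 2 of 12 women have no value.

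These figures are illustrative and not estimates for this trial. The direction, proportionally lowest where exposure is lowest, does not depend on the exact shape; the size does. In absolute terms the shortfall is at most about 70 ng·h/mL in that model, about 7% of 965. The consequence is for the reported exposure figure and its wording, not for the verdict against historical AUCs in the expected range.

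The conflict in Day 5 sampling times is certain from the text and needs no model.

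**What to change.** 1. Reconcile the Day 5 sampling times in Section 4.4 and the Lay Summary with the synopsis, Protocol Summary and Sections 1.7, 2.4 and 4.2. Do this first. On the Section 4.4 times the two runs proposed below both miss the true mean AUC(0-6) at full and half rectal exposure (743-779 against 886; 363-411 against 443).
2. In Sections 4.4 and 4.5.2, define the primary DHA AUC over the fixed sampled interval after the Day 5 dose (0-8 h if that schedule is kept). Include every evaluable woman and set below-limit values to 0. Repeat with them set to the limit as a sensitivity run. Describe the pair as an approximate bracket for mean AUC over that interval only, not for AUC to infinity or for individual women. Count time from the Day 5 dose.
3. Report the number of women with no quantifiable sample. Report AUC to infinity, half-life, CL/F and V/F only where the terminal phase meets a pre-stated criterion, with the number not estimable.
4. Word any conclusion of no exposure as below the limit of quantification (about 70 nM).

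**Cost.** Wording and a second AUC run on the same data, with no samples beyond the 8 h schedule. The downsides should be stated in the plan:
- The two runs differ visibly at low exposure (about 61 against 188 ng·h/mL at 10%).
- The upper run credits 8 × 19.9 = 159 ng·h/mL, 16.5% of 965, to a woman with no drug.
- The primary run still reads low against AUC to infinity (about 63% at 10%), though less so than the stated rule (35%).
- Some secondary parameters will be missing.
- If all 12 women are entirely below the limit, the primary run has mean 0 and SD 0 and the one-sample t-test cannot be computed. The plan should say that the count and the upper run are then reported instead.
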